### **c.8. Data Analysis**

**c.8.1. Overview.** As in the R34 study, [name] will design a customized web-based randomization, data entry and management system for this project. We will use Qualtrics, a widely used secure web-based software package to collect data. Therapist will also use Excel to enter de-identified fidelity and cost data. Data will be uploaded to Box. (see Protection of Human Subjects 5.1.1.a.). [name] will work closely with the PI on the development of the data management system and with the PI/ Co-Is in the data management/analysis of the psychological, physiological and cost-related data.

**c.8.2. General Analytic Plan.** Descriptive and graphical statistics will be used to summarize the data on all randomized patients and to confirm that there are no group or site differences ( $p < .10$ ) in baseline demographics and clinical characteristics. If, for example, site differences are detected, we will account for it by including site indicators as fixed effects in the model. Distributional assumptions will be checked and appropriate transformations or non-parametric methods will be applied as necessary. For Primary Aim 1, we will use methods that are based upon establishing equivalence or non-inferiority of outcomes across treatment arms. These methods are used classically to evaluate whether a new treatment or condition is not inferior to an existing treatment. In general, Generalized Linear Models (GLM) will be used throughout. These models account for deviation from normal assumption of the dependent variables and to control for baseline covariates including patients' demographics and corresponding child and parents assessment measures. For Primary Aim 2, GLM will be used to quantify the relation between the value of the tailoring variables and the propensity of not responding to Step One. For Primary Aim 3, latent difference score models (LDS) will be applied. We will mainly use SAS 9.3 and Mplus 7.1 for GLM and mediation analysis. For Primary Aim 4, a cost effectiveness analysis (CEA) will be performed. CEA measures the incremental cost per unit improvement in outcomes. In the absence of outcome differences, costs will be examined using GLM.

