**Primary Aim 4:** CEA examines the relative value of SC-TF-CBT (versus standard TF-CBT). CEA is performed from a societal perspective, meaning the costs to the health care system and the patient/parents are included. Treatment costs include direct (e.g., cost of therapy session), indirect (e.g., travel costs, missed work), and opportunity costs (e.g., value of lost time; see c.1.5. & c.7.4. for cost measures). CEA often incorrectly omits the opportunity cost of patient/parent time spent on therapy, phone support, and at-home parent-child meetings. Non-study mental health service costs include inpatient, outpatient, and school-based services and will be priced using the Florida Medicaid fee schedule. Research-specific costs (e.g., screening, research consent) for patients and staff are excluded. GLM will be used to examine differential treatment costs for SC-TF-CBT and standard TF-CBT. GLM can account for the likely skewed distribution of costs, differences in child characteristics, and a potential lack of independence within treatment locations. Incremental cost effectiveness ratios (ICER) are computed as incremental costs divided by incremental changes in morbidity/outcomes (symptom reduction and change in impairment/functioning). A single outcome measure (e.g., Quality Adjusted Life Years) might be preferable, but no established parameters for estimating morbidity in young children with trauma exist. If outcomes differ significantly, a non-parametric bootstrap with replacement method is used to generate a joint distribution of differential costs and outcomes. If outcomes do not differ, cost-effectiveness is determined by comparing treatment costs. Mean and median ICER ratios are reported as well as 95% confidence

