intervals. Cost-effectiveness acceptability curves examine the probability of falling below a variety of cost-effectiveness thresholds. In addition to the ICER approach, the net-benefit approach will be used to determine if findings are sensitive to method. If tailoring variables effectively distinguish children who respond to Step One, CEA will also be performed for children with low scores on tailoring variables. CEA will not be performed for children with high scores on the tailoring variables since the preliminary data indicate that standard TF-CBT is necessary for these children (c.1.2.). Race/ethnicity and gender differences in CEA will be assessed if treatment outcomes vary (see 6. Inclusion of Women and Minorities).

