## Amendment to the analysis plan 2.11.2022

**Aim 1.** We applied linear mixed-effect models (LME; SAS Institute Inc, 2015) with repeated measures to detect whether the two treatments performed differently at post-, 6- and 12-month assessments. Instead of 5% alpha we used a more stringent 2.5% alpha (Piaggio et al, 2012) for the non-inferiority analysis with the .41 margin. For the non-inferiority margin for the PCL-5, the clinically significant change threshold is 10 points although adult PTSD trials have used -5 (Foa et al., 2019) to -10 (Mathersul et al., 2019) points. We used -8.8 as the margin which was based on an expert panel and prior studies with adults (Acierno et al., 2017). Due to attrition (27.87%) being higher than planned (15%) and enrollment (N = 183) lower than the planned enrollment (N = 216), the power analysis was based on the actual randomization of 183 participants (SC-TF-CBT=91; standard TF-CBT=92).

**Aim 2.** We used backward stepwise logistic regression with predictors with  $p < .01$ . Besides predictors in the unadjusted model, demographics including children gender, age and race were included in the partially adjusted

model. In addition, three child primary outcomes were added for the full adjusted model.

**Aim 3.** Instead of LDS we used Linear mixed-effect models (LME) with repeated measures were used to detect whether the potential mechanisms of change declined significantly over time and whether the rate of change differed by treatment group with standard TF-CBT coded as 0 and Step One responders coded as 1. Further, we tested mediation and moderated mediation. If moderated mediation was not found mediation was tested with two regression equations: the first equation included mediators regressed on treatment condition and outcome variables at baseline; the second equation included outcomes regressed on treatment condition, mediators, and outcome variables at baseline. If there was no evidence of significant mediation, linear regression model (OLS) was applied to test the linear estimates as predictors for both outcome (TSCYC-PTS and CSDS-P).

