**Aim 4.** A cost comparison analysis of SC-TF-CBT and TF-CBT was performed instead of CEA, given the non-inferiority results. We used generalized linear models using a loglink to determine if differences in costs between the two treatments were statistically significant (two-tailed tests). Effect sizes were estimated based on the logged cost values and statistical significance was inferred via bootstrapped estimation (Algina et al., 2006).

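### Lower cost plus non-inferiority does not establish Hypothesis 4.1 (more cost-effective), yet amended Aim 4 keeps only a cost comparison and leaves the hypothesis unchanged

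*Combined protocol and SAP*

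**What the plan says.** Specific Aims heads Aim 4 as an examination of the economic cost of delivering the two treatments. Hypothesis 4.1 beneath it goes further and predicts that Stepped Care TF-CBT will be more cost-effective.

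The plan in c.8 branches on the outcome result. If outcomes differ: "If outcomes differ significantly, a non-parametric bootstrap with replacement method is used to generate a joint distribution" of cost and outcome differences. If not: "If outcomes do not differ, cost-effectiveness is determined by comparing treatment costs". Section c.8.2 agrees: "In the absence of outcome differences, costs will be examined using GLM". The end of Primary Aim 4 in c.8.3 adds two further tools: "Cost-effectiveness acceptability curves examine the probability of falling below a variety of cost-effectiveness thresholds", and "In addition to the ICER approach, the net-benefit approach" is to be used as a sensitivity check. It does not say whether these also apply when outcomes do not differ.

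The amendment of 2.11.2022 replaces the branch under Aim 4: "A cost comparison analysis of SC-TF-CBT and TF-CBT was performed instead of CEA, given the non-inferiority results". What remains is a log-link generalized linear model for costs and an effect size on logged costs. Under Aim 1 the amendment gives the non-inferiority test a 2.5% alpha with the 0.41 margin. Hypothesis 4.1 is not reworded.

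**The concern.** A cost-effectiveness statement weighs a cost difference against an outcome difference, with uncertainty in both. It reduces to cost alone only if the outcome difference can be taken as zero.

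Neither condition in the documents justifies that. A non-significant difference is compatible with a real deficit that the trial was too small to detect. Non-inferiority excludes deficits of 0.41 SD or more in one direction and leaves smaller ones open. A deficit small enough to be acceptable for Aim 1 is still a loss that an incremental ratio or a net benefit has to price.

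At stake is the Aim 4 conclusion. If lower cost is reported together with non-inferiority, Hypothesis 4.1 may be read as confirmed although nothing in the amended analysis has combined cost with outcome uncertainty.

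**Working it through.** **Inputs.** Margin 0.41 SD, and 92 per group with 80% power (c.9). One-sided test (c.8.3, Primary Aim 1). Alpha 2.5%, 183 randomised (91 and 92), attrition 27.87% (amendment, Aim 1). Pilot costs $906 and $2,094, a saving of $1,188, d = 2.01 (a.5 and c.1.4).

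**Step 1: reproduce the plan's figure.** With 92 per arm, SE = sqrt(2/92) = 0.1474 SD. Power at equal effects = Φ(0.41/0.1474 − 1.96) = 79.4%. This matches the stated 80% at one-sided 0.025. One-sided 0.05 would give 87.2%.

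**Step 2: sample sizes for the check.** 183 × (1 − 0.2787) = 132, or 66 per arm. This assumes that the attrition applies at the tested assessment and splits evenly. The other end of the range is all 91/92.

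**Step 3: what each condition lets through.** Unadjusted SE = sqrt(1/n1 + 1/n2), and d is the true deficit of Stepped Care.

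- Largest observed deficit declared non-inferior = 0.41 − 1.96 × SE.
- P(non-inferior) = Φ((0.41 − d)/SE − 1.96).
- P(not significant) = Φ(1.96 − d/SE) − Φ(−1.96 − d/SE).

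| | 66 per arm | 91/92 |
|---|---|---|
| SE (SD units) | 0.1741 | 0.1478 |
| 95% half-width | 0.341 | 0.290 |
| Largest deficit passing non-inferiority | 0.0688 | 0.1202 |
| P(non-inferior), d = 0 | 65% | 79% |
| P(non-inferior), d = 0.1 | 43% | 55% |
| P(non-inferior), d = 0.2 | 23% | 30% |
| P(not significant), d = 0.2 | 79% | 73% |
| P(not significant), d = 0.41 | 35% | 21% |

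These are for one outcome at one time point.

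**Step 4: baseline adjustment.** The planned models adjust for baseline. With an assumed baseline correlation of 0.5, each SE is multiplied by sqrt(1 − 0.25) = 0.866, giving 0.151 and 0.128. The largest passing deficits become 0.115 and 0.159 SD. P(non-inferior) at d = 0.2 becomes 28.5% and 37.5%.

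**Step 5: could it change the answer?** As an illustration, the break-even value of one SD of outcome is the saving divided by the deficit:

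- $1,188/0.0688 ≈ $17,300 per SD
- $1,188/0.1202 ≈ $9,900 per SD
- $1,188/0.41 ≈ $2,900 per SD

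Uncertainty matters as well. Take the cost SD as 1,188/2.01 ≈ $591, 66 per arm, no cost-outcome correlation and an observed deficit of 0.069 SD. The probability that Stepped Care is cost-effective at value λ per SD is Φ((1,188 − 0.069λ)/sqrt((0.1741λ)² + (0.1741 × 591)²)). This gives about 97% at $2,898, 83% at $5,000, 61% at $10,000 and 48% at $20,000.

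**The case against.** The strongest reply is that the amendment is coherent and modest. It calls its analysis a cost comparison, which fits Aim 4 as headed, and nowhere claims better cost-effectiveness. Its condition is also harder to meet under a true deficit than the one it replaced: at 0.2 SD, 23–30% against 79–73%. The margin, which is not disputed here, treats a 0.2 SD deficit as unimportant, and the pilot saving is large. All of this stands. What remains is that Hypothesis 4.1 was left in place with no analysis that answers it. A margin for clinical acceptability is also not a licence to set the effect to zero in an economic comparison.

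Four stronger readings are tempting but not supported.

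- A reader might infer that any of the many tested outcomes could have opened the cost-only route. Section c.8.3 ties the cost-effectiveness ratio to symptoms and to impairment or functioning, and c.6.1 and c.6.6 identify TSCYC-PTS and CSDS-P as primary measures. The outcomes are therefore reasonably clear. The time point and the handling of mixed results are missing detail.
- The amendment's Aim 2 sentence, "In addition, three child primary outcomes were added for the full adjusted model", might look like a conflict over which results count. It describes covariates in a logistic model and has no bearing on Aim 4.
- A reader might infer that c.8.3 rules out net benefit and acceptability curves when outcomes do not differ. The text leaves that open. Only the amendment, by replacing the cost-effectiveness analysis, settles it.
- A reader might infer that Stepped Care is not cost-effective. Nothing here shows that.

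**Conclusion.** The point holds. Hypothesis 4.1 is not answered by a cost comparison, whether the condition is a non-significant outcome difference (c.8.2, c.8.3) or non-inferiority within 0.41 SD (amendment). An observed deficit of up to 0.07–0.12 SD passes non-inferiority, with the 95% interval reaching 0.41 SD. A true 0.2 SD deficit passes on one outcome in 23–30% of trials, or 28.5–37.5% with an assumed baseline correlation of 0.5.

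These figures treat the comparison as a two-mean test. The repeated-measures model will differ somewhat, and 66 per arm is an assumption. The dollar figures are illustrative: the pilot costs excluded other services, and the documents give no value per unit of outcome. They show that a large saving may well outweigh a small deficit, and that the answer depends on that value.

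The cost result itself is not in question. The weakness was already in c.8.3, so the amendment should not be read as having created it.

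**What to change.** Under Aim 4 of the amendment:

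1. Keep the log-link model and the logged-cost effect size as the cost result.
2. Add, labelled post hoc, the joint cost-outcome analysis described in c.8.3, run whatever the outcome test shows. Use TSCYC-PTS and CSDS-P at one named time point, with costs over the same period: the time-tracking system for the treatment phase, plus the cost questionnaire (CCI) and the service-use interview through follow-up. Table 1 collects time tracking only at sessions, meetings or activities, and no recall windows are given, so state how costs are accumulated.
3. Bootstrap children within arm, keeping each child's cost and outcome paired. Allow for treatment location, which c.8.3 raises, and handle missing data with the multiple imputation of c.10.
4. Report the dollar cost difference, the incremental effect with its 95% interval, net benefit, and an acceptability curve over a stated range. The curve is descriptive, since no threshold is specified.

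If items 2 to 4 are not done, word the Aim 4 conclusion as *lower cost, with outcomes non-inferior within 0.41 SD* on the named outcomes and time point, and make no claim of better cost-effectiveness.

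The cost is analyst time on data already collected, a post-hoc label, and a result that may be less clear-cut than the cost difference alone. The fallback needs only a change of text.

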## 5.1 PROTECTION OF HUMAN SUBJECTS

### 5.1.1 Risks to Human Subjects

#### a. Human Subjects Involvement, Characteristics, and Design

Participants will be 216 children ages 4 to 12 years who have been exposed to traumatic event(s) and who are experiencing at least five PTSD symptoms. Parents/guardians must be able to provide written consent in order for their child to participate, and the parent/guardian must be willing to participate. Male and female parents and children will be included. There are no participant restrictions on ethnicity, social background, or gender. Study participation is entirely voluntary. If at any time a participant wishes to discontinue study participation, they can notify the PI and the participant will be withdrawn from the study at that time without any adverse consequences. It is necessary to include children in this research because the study aims focus on how to optimize the efficiency and cost-effectiveness of Stepped Care TF-CBT, a personalized adaptive intervention for traumatized children ages 4 to 12 years, under “real world” settings (i.e., in community mental health clinics).

Recruitment will occur at two community mental health clinics in Florida that specialize in mental health treatment for children who have experienced trauma: The Crisis Center of Tampa Bay (CCTB; Hillsborough County) and Pasco Kids First (PKF; Pasco and Hernando Counties). A back-up agency, Suncoast Center Inc (Pinellas County). Children’s Home Society Duval, Clay, Baker, Nassau, and St. John) USF St. Petersburg Family Study Center (Pinellas County) and Directions for Living (Pinellas County) will be involved if recruitment goals are not being met (see Other Attachment). The role of these sites will be to recruit patients, coordinate study procedures with the Project Coordinator, comply with all study procedures and Institutional Review Board (Ebert, #51) requirements, and provide study treatment. Parents/guardians who seek trauma-focused services at these two/three community centers and have children between the ages of 4 to 12 years will be informed about the study and if interested, participate in a brief phone screening prior to setting up an assessment. Consistent with our approved study protocol implemented for our NIMH R34 Stepped Care TF-CBT grant, data will be obtained on site at the community centers. These centers currently provide psychotherapy and comply with confidentiality procedures consistent with agency policies including being compliant with the Health Insurance Portability and Accountability Act (HIPAA). For the proposed study, participants and/or research staff (e.g., independent evaluator, graduate research assistant, therapists) will enter scale responses directly into Research Electronic Data Capture (Qualtrics™) software system. Qualtrics™ is a secure web application (the site is encrypted using SSL and is backed up nightly) designed to manage on-line surveys and databases for clinical trials. Data captured in Qualtrics™ can be easily exported in statistical packages such as Mplus, SAS and SPSS. USF is an institutional partner of Qualtrics™. Subjects will have access only to complete their own scales. Fidelity ratings will be entered into Excel by the study therapists which can be easily converted to SPSS. All computer-generated data will be maintained in password-protected computers. Any measures collected on paper such as the mechanism of change measures will be double data-entered into Qualtrics™ and paper documents will be stored in the PIs office in locked filing cabinets at USF. No patient names will be recorded on assessment information as each participant will be assigned a record number. A separate record linking the code numbers to participant identifiers will be kept in a locked file, completely separate from the data.

The study design consists of a randomized clinical trial where all participants will receive empirically-informed treatment based on TF-CBT, a well-established treatment. Specific inclusion and exclusion criteria are listed in Research Strategy (see Research Strategy section c.2.2.). The exclusion of non-English speaking patients is due to methodological issues and costs of including children and parents who speak other languages (e.g., measures and the parent-child workbook would need to be translated, and study staff would need to speak other languages). If findings are significant, the next step in the development of Stepped Care TF-CBT would be to provide the protocol in other languages (e.g., Spanish). Of note, in our pilot trials on Stepped Care TF-CBT, 35.8% of the child participants were Hispanic/Latino. In addition, any medication issues related to study exclusion will be discussed with the consulting psychiatrist, [name]., who may contact the prescribing physician (see 5.1.1. c.). In our previous trials on Stepped Care TF-CBT, only 1.4% (6 of 419) screened out due to medication related factors.

Patients will be randomly assigned to either Stepped Care TF-CBT or standard TF-CBT. Once the patient has enrolled in treatment, we will allow for up to two contact sessions outside of the standardized treatment protocols regardless of condition. This flexibility of additional sessions to address individualized treatment needs is common in community mental health practice and this flexibility will be used to maximize retention. Other strategies to maximize retention include setting clear expectations about the research process, compensation

for assessments, transportation to the center for the assessments (if needed) and supervision of siblings during appointments (if needed).

### **b. Sources of Materials**

The sources of research material obtained from each human subject will be in the form of information gathered specifically for research purposes. This will include data from the psychological assessments, behavioral rating scales, physiological measures (e.g., heart rate and skin conductance), cost-related data, and session/interview content. Data obtained from this study will be from individual meetings with the parent and child where they will be asked the questions from the listed measures or IE or therapist ratings of adherence and time. Data gathered from parents will be reports about their children or data about themselves. Data for treatment integrity will be obtained from videotaped therapy sessions (with the permission written consent from the parent and the therapist).

To protect subjects' confidentiality, only authorized persons from the University of South Florida, the sponsor (NIMH), and the USF Institutional Review Board will have the right to review research records. Confidentiality of those records will be protected to the full extent permitted by law. Research records will be kept secured in a locked archive and will not be released without the subject's consent unless required by law (e.g., suspected abuse) or a court order. When the results of this research are published or presented at scientific meetings, the identity of subjects will not be disclosed.

### **c. Potential Risks POTENTIAL RISK**

**Note.** While [REDACTED] is on [REDACTED] [name] will serve in [REDACTED] role.

**Please note, on 10/12/18 IRB approved an agreement where Baylor College of Medicine/PI, [name] will be relying on USF IRB Approval. See IRB letter dated 10/12/18, RE: Approval to Proceed Ext00000337**

Potential risks associated with this study may occur due to parents and children participating in assessments, participating in psychotherapy, and minimal intervention during the follow-up period. The potential risk of participating in the evaluations may result in discomfort discussing traumatic experiences, discomfort answering other subjectively difficult questions, or discomfort due to the time needed to complete the assessments. With regard to potential discomfort in answering questions, our experience indicates that many people welcome the opportunity to discuss their experiences with a trained clinician. The parents who are consenting to participate are aware that this study is for children who experienced a traumatic event and parents often welcome the opportunity to talk with a clinician about what has happened. If at any time a parent or child becomes overwhelmed during any assessment, we will pause or stop depending on the degree of distress. It is possible that the adhesives for the skin conductance test may cause skin irritation, and parents and children will be made aware of this possibility via the written consent and assent process and verbally prior to administering the tests. These electrodes are non-invasive and relatively unobtrusive. During the assessments, breaks will be given as often as possible to decrease boredom and physical/psychological discomfort.

If a child's symptoms worsen, whether the deterioration is linked to the treatment or not, we will discuss with the parent clinically appropriate alternatives, such as increasing therapist-directed therapy sessions during Step One (additional sessions are included in the protocol for situations where children need more therapy), stepping up to Step Two to receive therapist-directed TF-CBT, having a child undergo psychiatric evaluation to determine mental health status, or discontinuing the study and engaging community resources for additional help. Two additional therapy sessions are included in the study protocol for those situations where crises or worsening of symptoms occur (examples may include sexual aggression, danger to self or other). If clinical worsening occurs during treatment, the therapist will discuss this in team meetings. The therapist, parent and child (ages 7-12) will complete the CGI-I at each visit. As used in our pilot studies on Stepped Care TF-CBT, clinical worsening is operationalized as a therapist, parent, child or IE rating of 8 ("very much worse"), 7 ("much worse") or three consecutive ratings of 6 ("minimally worse") on the CGI-I. Three consecutive ratings of minimally worse instead of one rating of minimally worse was stated because it is possible that some children may exhibit some regression when processing the trauma narrative, thus resulting in a temporary minimally worse rating. As previously planned, the parent, child, and IE will complete the CGI-I at post-treatment and follow-up. The therapist will complete the CGI-I after every face-to-face session and one time a week via phone sessions during

Step One to consistently monitor possible clinical worsening. If clinical worsening occurs, the PI will consult with [name] about the appropriate course of treatment, which may include additional sessions, having a child undergo psychiatric evaluation to determine their mental health status and/or discontinuing the study and seeking additional help from community resources. If an additional session is indicated, the therapist will plan for the individualized session during the weekly team meeting so that an individualized targeted plan for the session(s) can be developed based on the noted concern(s). Including additional sessions does not compromise the integrity of the intervention, while balancing the well-being of participants. On balance, the majority of families in our pilot studies on Stepped Care TF-CBT and standard TF-CBT reported symptom reduction and improvement in functioning following participation.

[name]. Professor and Rothman Endowed Chair, Director, Rothman Center for Pediatric Neuropsychiatry at the University of South Florida has agreed to be involved as an independent consultant who would be available to consult with the PI to make judgments about the appropriate course of treatment for children with ratings of clinical worsening. [name] will not know treatment assignment. [name] worked with [name] on the NIMH R34 Stepped Care for Young Children study in this capacity where she reviewed cases with clinical worsening (4 occurrences of 53 children enrolled in treatment) or clinical concerns (5 occurrences of 53 children enrolled) such as encopresis, passive suicidal ideation, or inappropriate boundaries with other children. [name] also met quarterly with Drs. [name] (PI) and [name] (Co-I) to discuss tolerability and safety. Through this work, Drs. [name] and [name] have established a strong working relationship. [name] (Co-I) also has a long collaborative relationship with [name] in the Departments of Pediatrics and Psychiatry at the Rothman Center for Pediatric Neuropsychiatry. [name] is board certified in child and adolescent psychiatry and general psychiatry, has a Master's degree in Clinical Investigation, and has considerable experience conducting federally-funded clinical trials with children (e.g., 1R01MH078594-01; see [name] biosketch).

While it is possible that the viewing the brief segments of the child's session via video will affect the parent's distress level, parental distress about the child's trauma and depression did not mediate the effect of treatment (TAU and TF-CBT) on child PTSD symptoms, although there was an effect on child depression. Sharing and discussing with the parent what the child completed in therapist-led session is current protocol for both treatments, and similar procedures have been used in previous trauma-focused clinical trials with children 3 to 12 (PI: [name], R34MH070827-01A1; 1RC1MH-088969-01). Research has shown that parent distress about the child's trauma improved during participation in TF-CBT. If parents experience discomfort during the treatment, we will provide supportive counseling as part of the treatment. However, if parent distress continues and psychiatric attention is needed, parents will be provided with a list of community mental health resources. Parent participation in individual therapy outside of the study is not an exclusion criterion. If a parent participates in other therapy we will document this but will not exclude parents who are participating in their own therapy since we are not providing parent-focused mental health treatment. The treatment is child-focused although it is likely that some parents will benefit psychologically from their child's participation in treatment as well as from the supportive counseling that will be provided in both treatment arms.

